6.3. Exploratory Efficacy Endpoints

6.3.1. Definition of Exploratory Efficacy Endpoints

PPD

6.3.2. Analysis Methods for Exploratory Efficacy Endpoints

PPD

6.4. Changes From Protocol-Specified Efficacy Analyses

PPD

7. SAFETY ANALYSES

7.1. Adverse Events and Deaths

7.1.1. Adverse Event Dictionary

Clinical and laboratory adverse events (AEs) will be coded using the current version of MedDRA. System organ class (SOC), high-level group term (HLGT), high-level term (HLT), preferred term (PT), and lower-level term (LLT) will be provided in the AE dataset.

7.1.2. Adverse Event Severity

Adverse events are graded by the investigator as Grade 1, 2, 3, or 4 according to toxicity criteria specified in the protocol. The severity grade of events for which the investigator did not record severity will be categorized as “missing” for tabular summaries and data listings and the most severe will be considered (for sorting purpose only) in data presentation.

7.1.3. Relationship of Adverse Events to Study Drug

Related AEs are those for which the investigator selected “Related” on the AE eCRF to the question of “Related to Study Treatment”. Events for which the investigator did not record relationships to study drug will be considered related to study drug for summary purposes. However, by-subject data listings will show the relationship as missing from that captured on the CRF.

7.1.4. Serious Adverse Events

Serious adverse events (SAEs) will be identified and captured as SAEs if AEs met the definitions of SAE specified in the study protocol. Serious adverse events captured and stored in the clinical database will be reconciled with the SAE database from the Gilead Pharmacovigilance and Epidemiology Department before database finalization.

7.1.5. Treatment-Emergent Adverse Events

7.1.5.1. Definition of Treatment Emergent

Treatment-emergent adverse events (TEAEs) are defined as one or both of the following:

- Any AEs with an onset date on or after the study drug start date and no later than 30 days after permanent discontinuation of study drug.
- Any AEs leading to premature discontinuation of study drug.

7.1.5.2. Incomplete Dates

If the onset date of the AE is incomplete, then the month and year (or year alone if month is not recorded) of onset determine whether an AE is treatment emergent, as long as the AE stop date is not prior to the first dose date of study drug. The event is considered treatment emergent if both of the following 2 criteria are met:

- The AE onset and end dates are the same as or after the month and year (or year) of the first dose date of study drug
- The AE onset date is the same as or before the month and year (or year) of the 30th day after the date of the last dose of study drug

An AE with completely missing onset and stop dates, or with the onset date missing and a stop date later than the first dose date of study drug, will be considered to be treatment emergent.

7.1.6. Summaries of Adverse Events and Deaths

A brief high-level summary of TEAEs will be provided by the number and percentage of subjects who had the following: any AE; any AE of Grade 3 or above; any AE of Grade 2 or above; any treatment-related AE; any treatment-related AE of Grade 3 or above; any treatment-related AE of Grade 2 or above; any SAE; any treatment-related SAE; any AE that led to premature discontinuation of study drug. All deaths (including those that are treatment emergent and those that are not treatment emergent) observed during the study will also be summarized and included in this table.

Adverse event summaries will provide the number and percentage of subjects with TEAEs by SOC and PT based on the Safety Analysis Set as follows:

- All AEs
- AEs of Grade 3 or above
- AEs of Grade 2 or above
- All treatment-related AEs
- Treatment-related AEs of Grade 3 or above
- Treatment-related AEs of Grade 2 or above
- All SAEs
- All treatment-related SAEs
- All AEs leading to premature discontinuation of study drug
- All AEs leading to interruption of study drug
- Deaths

Multiple events will be counted only once per subject in each summary. Adverse events will be summarized and listed first in alphabetic order of SOC and then by PT in order of descending incidence within each SOC. In summaries by severity grade, the most severe grade will be used for those AEs that occurred more than once in an individual subject during the study.

In addition to the above summary tables, TEAEs will be summarized by PT only, in order of descending incidence for:

- AEs that occurred in at least 5% of subjects
- AEs of Grade 3 or above
- All treatment-related AEs
- All SAEs
- AEs leading to premature discontinuation of study drug
- All AEs leading to interruption of study drug

In addition to the summaries described above, data listings will be provided for the following:

- All AEs (with a variable indicating whether the event is treatment emergent)
- AEs of Grade 3 or above
- SAEs
- Deaths
- AEs leading to premature discontinuation of study drug

7.2. Laboratory Evaluations

Laboratory data collected during the study will be analyzed and summarized using both quantitative and qualitative methods. Summaries of laboratory data will be provided for the Safety Analysis Set and will include data collected up to the last dose of study drug plus 30 days for subjects who have permanently discontinued study drug or all available data at the time of the database snapshot for subjects those who were ongoing at the time of an interim analysis. The analysis will be based on values reported in conventional units. When values are below the limit of quantitation, they will be listed as such, and the closest imputed value will be used for the purpose of calculating summary statistics. For example, if “< 0.2” was recorded, a value of 0.1 will be used for the purpose of calculating summary statistics; if “< 0.1” was recorded, a value of 0.09 will be used for the purpose of calculating summary statistics.

A by-subject listing for laboratory test results will be provided by subject ID number and visit in chronological order for hematology, serum chemistry, and urinalysis separately. Values falling outside of the relevant reference range and/or having a severity grade of 1 or higher on the Gilead Grading Scale for Severity of Adverse Events and Laboratory Abnormalities will be flagged in the data listings, as appropriate.

No inferential statistics will be generated.

7.2.1. Summaries of Numeric Laboratory Results

Descriptive statistics (n, mean, SD, median, Q1, Q3, minimum, and maximum) will be provided for ALT, AST, total bilirubin, alkaline phosphatase, hemoglobin, reticulocytes, white blood cell (WBC), neutrophils, lymphocytes, platelets, and INR as follows:

- Baseline values
- Values at each postbaseline time visit
- Change from baseline at each postbaseline visit

A baseline laboratory value will be defined as the final assessment performed on or prior to the date/time of first dose of study drug. Change from baseline to a postbaseline visit will be defined as the visit value minus the baseline value. The mean, median, Q1, Q3, minimum, and maximum will be displayed to the reported number of digits; SD to the reported number of digits plus 1.

Median (Q1, Q3) of the observed values for ALT, AST, total bilirubin, alkaline phosphatase, hemoglobin, reticulocytes, RBC, WBC, neutrophils, lymphocytes, and platelets will be plotted using a line plot by visit.

In the case of multiple values in an analysis window, data will be selected for analysis as described in Section 3.8.3 (Selection of Data in the Event of Multiple Records in a Window).

7.2.2. Graded Laboratory Values

The Gilead Grading Scale for Severity of Adverse Events and Laboratory Abnormalities will be used for assigning toxicity grades (0 to 4) to laboratory results for analysis. Grade 0 includes all values that do not meet the criteria for an abnormality of at least Grade 1. Some laboratory tests have criteria for both increased and decreased levels; analyses for each direction (ie, increased, decreased) will be presented separately.

7.2.2.1. Treatment-Emergent Laboratory Abnormalities

Treatment-emergent laboratory abnormalities are defined as values that increase at least 1 toxicity grade from baseline at any postbaseline time point, up to and including the date of last dose of study drug plus 30 days for subjects who permanently discontinued study drug, or all available data in the database snapshot for subjects who were still on treatment at the time of an interim analysis. If the relevant baseline laboratory value is missing, then any abnormality of at least Grade 1 will be considered treatment emergent.

7.2.2.2. Summaries of Laboratory Abnormalities

Laboratory data that are categorical will be summarized using the number and percentage of subjects in the study with the given response at baseline and each scheduled postbaseline visit.

The following summaries (number and percentage of subjects) for treatment-emergent laboratory abnormalities will be provided by analyte; subjects will be categorized according to the most severe postbaseline abnormality grade for a given analyte:

- Graded laboratory abnormalities
- Grade 3 or above laboratory abnormalities

For all summaries of laboratory abnormalities, the denominator is the number of subjects with nonmissing postbaseline values up to 30 days after last dose for the laboratory parameter of interest.

A by-subject listing of treatment-emergent Grade 3 or above laboratory abnormalities will be provided by subject ID number and visit in chronological order. This listing will include all test results that were collected throughout the study for the analyte of interest, with all applicable severity grades or abnormal flags displayed.

7.3. Body Weight, Height, and Vital Signs

Vital signs (systolic and diastolic blood pressure [mmHg], pulse [beats/min]) at each visit, and change from baseline at each visit will be summarized for the Safety Analysis Set using descriptive statistics (n, mean, SD, median, Q1, Q3, minimum, and maximum). The baseline value will be defined as the last available value collected on or prior to the date/time of first dose of study drug. Change from baseline to a postbaseline visit will be defined as the postbaseline value minus the baseline value.

In the case of multiple values in an analysis window, data will be selected for analysis as described in Section 3.8.3 (Selection of Data in the Event of Multiple Records in a Window). No inferential statistics will be generated.

A by-subject listing of vital signs (systolic and diastolic blood pressure [mmHg], pulse [beats/min], respiration [breaths/min], and body temperature [°C]) will be provided by subject ID number and visit in chronological order. In the same manner, a by-subject listing of body weight, height, and BMI at baseline will be provided separately.

7.4. Prior and Concomitant Medications

Medications collected at screening and during the study will be coded using the current version of the World Health Organization (WHO) Drug dictionary. The medications will be categorized as prior or concomitant using the following definitions:

- Prior medications: any medications taken and stopped prior to or on the date of first study drug administration
- Concomitant medications: any medications taken after the date of first study drug administration and up to the last dosing date of study drug

Concomitant medications will be summarized by preferred name using the number and percentage of subjects for each treatment group. A subject reporting the same medication more than once will be counted only once when calculating the number and percentage of subjects who received that medication. The summary of concomitant medications will be ordered by preferred term in descending frequency. For drugs with the same frequency, sorting will be done alphabetically.

Summaries will be based on the Safety Analysis Set. No inferential statistics will be generated.

For purposes of analysis, any medication with a stop date that is on or prior to the initial study drug dosing date or a start date that is after the last study drug dosing date will be excluded from a concomitant medication summary. If a partial stop date is entered, any medication with the month and year (if day is missing) or year (if day and month are missing) prior to the initial study drug dosing date will be excluded from the concomitant medication summary. If a partial start date is entered, then any medication with the month and year (if day is missing) or year (if day and month are missing) after the study drug stop date will be excluded from the concomitant medication summary. Medications with completely missing dates will be included in the concomitant medication summary.

All prior and concomitant medications (other than per-protocol study drugs) will be provided in a by-subject listing sorted by subject ID number and administration date in chronological order.

7.5. Electrocardiogram Results

A by-subject listing for ECG assessment results at Screening will be provided by subject ID number.

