- To evaluate the kinetics of circulating HCV RNA during treatment and after cessation of treatment
- To evaluate the emergence of viral resistance to SOF, VEL, and VOX during treatment and after cessation of treatment

Study Design:	
Approximately 50 subjects with chronic HCV infection who did not achieve an SVR in a prior Gilead-sponsored HCV treatment study will be enrolled.
 
Subjects will receive SOF/VEL/VOX FDC (400/100/100 mg) once daily with food for 12 weeks.

Number of Subjects Planned:	Approximately 50 subjects.
Target Population:	Adults with chronic hepatitis C virus (HCV) infection who participated in a prior Gilead-sponsored HCV treatment study and did not achieve SVR
Duration of Treatment:	Subjects will be treated for 12 weeks.
Diagnosis and Main Eligibility Criteria:	
Chronically HCV-infected male and non-pregnant/non-lactating female subjects aged 18 years or older who did not achieve SVR in a prior Gilead-sponsored HCV treatment study.
 
Refer to Section 4.2 and 4.3 for detailed Inclusion and Exclusion Criteria.

Study Procedures/ Frequency:	
All subjects will complete the following study visits: Screening, Day 1, and on-treatment visits at the end of Weeks 2, 4, 8, and 12. Posttreatment visits will occur at Weeks 4 and 12 after last dose of study drug.
 
Screening assessments will include physical examination, medical history, height, weight, vital signs, 12-lead electrocardiogram (ECG), adverse events related to Screening procedures, concomitant medications, safety laboratory tests (including hematology, chemistry, and coagulation), HCV RNA, HCV genotyping, serology (HCV, HBV, HIV), hemoglobin A1c (HbA1c), assessment of the presence or absence of cirrhosis (including Fibrotest[®]), screening for hepatocellular carcinoma (HCC) for subjects with cirrhosis, serum β-human chorionic gonadotropin (β-hCG) (females of child-bearing potential only), IL28B genotyping, urinalysis, and urine drug screen.
 
On-treatment assessments include adverse events (AEs), concomitant medications, study drug dispensation and pill count, physical examination, weight, vital signs, safety laboratory tests, HCV RNA, pharmacokinetic samples (after Day 1), and urine pregnancy tests (females of childbearing potential only). Samples for the viral RNA sequencing/phenotyping will be collected at Day 1 and every visit thereafter. Single 12-lead ECGs will be collected at Early Termination (ET), if applicable.

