1.2.2.4.3. Overall Safety of SOF/VEL/VOX

The overall safety of SOF/VEL/VOX is based on pooled Phase 3 clinical trial data from DAA-experienced subjects (POLARIS-1 and POLARIS-4) and DAA-naïve subjects (POLARIS-2 and POLARIS-3) with HCV infection (without cirrhosis or with compensated cirrhosis) including:

- 445 subjects who received SOF/VEL/VOX for 12 weeks
- 611 subjects who received SOF/VEL/VOX for 8 weeks
- 700 subjects who received SOF/VEL for 12 weeks
- 152 subjects who received placebo for 12 weeks

The proportion of subjects who permanently discontinued treatment due to AEs was 0.2% for subjects receiving SOF/VEL/VOX for 12 weeks. There were no subjects receiving SOF/VEL/VOX for 8 weeks who permanently discontinued treatment due to AEs.

The most frequent AEs occurring in subjects receiving SOF/VEL/VOX for 12 weeks were headache (26%), fatigue (22%), diarrhea (19%), and nausea (13%). The rates of AEs, except diarrhea and nausea, were similar in all groups in the pooled Phase 3 clinical trial data. Diarrhea and nausea occurred most frequently in subjects received SOF/VEL/VOX.

In the Phase 3 trials, Grade 1 increases in total bilirubin were observed in 4% of subjects without cirrhosis and 10% of subjects with compensated cirrhosis, due to inhibition of OATP1B1 and OATP1B3 by voxilaprevir. Total bilirubin levels decreased after completing SOF/VEL/VOX treatment. No subjects experienced jaundice.

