3.4. Discontinuation Criteria

If a subject discontinues study dosing (for example, as a result of an AE, every attempt should be made to keep the subject in the study and continue to perform the required study-related follow-up procedures (see Section 6.5). If this is not possible or acceptable to the subject or investigator, the subject may be withdrawn from the study.

When medically feasible, the medical monitor must be consulted prior to subject discontinuation.

Study drug must be discontinued in the following instances:

- Intercurrent illness that would, in the judgment of the investigator, affect assessments of clinical status to a significant degree. Following resolution of intercurrent illness, the subject may resume study dosing at the discretion of the investigator
- Unacceptable toxicity or toxicity that, in the judgment of the investigator, compromises the ability to continue study-specific procedures or is considered to not be in the subject's best interest
- Virologic failure (as defined in Section 3.5)
- Pregnancy of female subject (refer to Appendix 4)
- Significant protocol violation that impacts subject safety
- Subject request to discontinue for any reason; it is important to determine whether the withdrawal of consent is primarily due to an AE, lack of efficacy, or other reason

- Subject noncompliance
- Discontinuation of the study at the request of Gilead, regulatory agency or an Institutional Review Board (IRB)/Independent Ethics Committee (IEC)

All subjects who terminate early will complete the ET visit and posttreatment Week 4 and 12 visits.

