8.2. Analysis Conventions

All individual subject data will be listed as measured. All statistical summaries and analyses will be performed using SAS software (SAS Institute, Cary, North Carolina, USA).

All continuous endpoints will be summarized using an 8-number summary (n, mean, standard deviation [SD], median, 1st quartile [Q1], 3rd quartile [Q3], minimum, maximum). All categorical endpoints will be summarized by the number and percentage of subjects who meet the endpoint definition.

Last dose of study drug refers to the last dose of SOF/VEL/VOX FDC and will be used in the definition of treatment-emergent AEs and laboratory abnormalities as well as the efficacy endpoints of SVR at various post-treatment time points.

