8.6.4. Other Safety Evaluations

Individual data for 12-lead ECG, vital sign measurements will be listed by subject and incidence of events/abnormalities will be summarized descriptively by study visit as appropriate.

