3. GENERAL CONSIDERATIONS FOR DATA ANALYSES

Analysis results will be presented using descriptive statistics. For categorical variables, the number and percentage of subjects in each category will be presented; for continuous variables, the number of subjects [n], mean, standard deviation [SD] or standard error [SE], median, first quartile [Q1], third quartile [Q3], minimum, and maximum will be presented.

Data collected in the study will be presented in by-subject listings for all subjects in the Safety Analysis Set, unless otherwise specified. All by-subject listings will be presented by subject identification (ID) number in ascending order, unless otherwise specified.

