7.7. Changes From Protocol-Specified Safety Analyses

There are no deviations from the protocol-specified safety analyses.

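### Does an ECG listing worded for Screening only leave the Early Termination ECG out of the report?

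*SAP*

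**What the plan says.** SAP 7.5 names one ECG output: "A by-subject listing for ECG assessment results at Screening will be provided by subject ID number".

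The ECG schedule is wider. The Protocol synopsis states: "Single 12-lead ECGs will be collected at Early Termination (ET), if applicable". The procedures tables in Protocol Appendix 2 and SAP Appendix 1 mark the 12-lead ECG at Screening and at ET. Protocol 3.4 sends early stoppers to that visit: "All subjects who terminate early will complete the ET visit and posttreatment Week 4 and 12 visits".

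On reporting, Protocol 8.2 sets a general rule: "All individual subject data will be listed as measured". Protocol 8.6.4 says of individual data that "12-lead ECG, vital sign measurements will be listed by subject and incidence of events/abnormalities will be summarized descriptively by study visit as appropriate". Neither names a visit. The SAP has its own default in section 3: "Data collected in the study will be presented in by-subject listings for all subjects in the Safety Analysis Set, unless otherwise specified". SAP 7.7 closes the safety chapter with "There are no deviations from the protocol-specified safety analyses".

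**The concern.** Safety and tolerability form one of the two primary objectives, and the ET ECG is the only ECG scheduled once dosing has started. A plan that lists the pre-dose tracing and omits the post-dose one would report the less informative of the two. The subjects concerned are those who stopped early, including any who stopped for an adverse event, and such stops are the primary safety endpoint in Protocol 8.1.4.

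The neighbouring sections make the wording stand out. SAP 7.2 and 7.3 list laboratory results and vital signs by subject and visit; only the ECG section ties its listing to a single visit. The default in SAP 3 gives way where a section specifies otherwise, and naming Screening could be taken as doing so. On that reading the SAP is narrower than Protocol 8.6.4, and the statement in SAP 7.7 would be wrong.

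**Working it through.** **1. The texts side by side**

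| Source | Which ECGs | Visit limit |
|---|---|---|
| Protocol synopsis and Appendix 2; SAP Appendix 1 | collected at Screening and, if applicable, ET | not a reporting rule |
| Protocol 8.2 | all individual data listed | none |
| Protocol 8.6.4 | individual ECG data listed; incidence summary where appropriate | none on the listing |
| SAP 3 | all collected data listed | none, unless a section specifies otherwise |
| SAP 7.5 | Screening results listed | Screening named; nothing said about other visits |

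SAP 7.5 promises one listing. It does not say that other ECGs will be left out. Two readings are therefore open: the default in SAP 3 covers the ET records, or 7.5 displaces that default. Under the first, SAP 7.7 is correct as it stands. The text does not establish the second.

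**2. How many ET ECGs to expect**

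The plan gives no figure for this, so there is none to reproduce. The inputs come from Protocol 1.2.2.4.

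- Subjects on 12-week SOF/VEL/VOX in POLARIS-1 and POLARIS-4: 263 + 182 = 445.
- Adverse event stops in those arms: "The proportion of subjects who permanently discontinued treatment due to AEs was 0.2% for subjects receiving SOF/VEL/VOX for 12 weeks". One subject fits this figure, since 1/445 = 0.22%.
- Stops for other reasons, all arms of both studies: 1 lost to follow-up and 1 for lack of efficacy. Their arms are not stated.
- Early stops on 12-week SOF/VEL/VOX therefore number between 1 (neither of those two in these arms) and 1 + 2 = 3 (both).

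Assume that this rate p carries over to about 50 subjects and that each early stop yields one ET ECG. The expected number is 50p, and the chance of at least one is 1 − (1 − p)^50.

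| Rate p | Expected ET ECGs in 50 | Chance of at least one | Chance of none |
|---|---|---|---|
| 1/445 = 0.22% | 0.11 | 10.6% | 89.4% |
| 3/445 = 0.67% | 0.34 | 28.7% | 71.3% |
| 2/333 = 0.60% (POLARIS-4, all arms) | 0.30 | 26.0% | 74.0% |
| 5/415 = 1.20% (POLARIS-1, all arms) | 0.60 | 45.5% | 54.5% |

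The last two rows include SOF/VEL or placebo subjects and only show the spread; the first two match the regimen. A subject lost to follow-up may have no ET ECG at all, so the upper figures are generous. In every row, no ET ECG is more likely than one or more.

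**3. What a Screening-only listing would lose**

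- Protocol 6.7.7 has the investigator review each tracing as it is recorded.
- Under Protocol 7.1.3, an abnormal ECG accompanied by signs or symptoms is recorded as an adverse event or SAE if it meets the definition. SAP 7.1.6 lists all adverse events.
- The primary safety endpoint is counted from adverse events that lead to permanent discontinuation, not from ECG listings.
- The incidence summary in Protocol 8.6.4 applies only where appropriate. With probably no ET record or one, there is nothing to summarise by visit.

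What remains is an ET tracing that gave rise to no adverse event, in perhaps one subject, shown or not shown in a descriptive listing.

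**The case for a change.** The best case for a change is that it would cost one phrase and need no new data. A programmer who works section by section could take 7.5 literally and produce a Screening-only listing. SAP 3.8.3 also defines an ECG baseline, which serves little purpose if no later ECG is reported. ECGs could arise at unscheduled visits too, since Protocol 6.6 leaves assessments there to the investigator's discretion, and a Screening-only listing would miss those as well.

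Part of this stands: the sentence in 7.5 is narrower than the schedule, and the literal reading is possible. It does not show a departure from the protocol, because two general rules, one in each document, already call for all individual data to be listed and 7.5 contains no words of exclusion. Nor does the cheapness of an edit create a need for one. Whichever reading is applied, no table, estimate, interval or conclusion changes. The appeal to the primary safety objective carries little weight here, because the endpoint that serves it does not use ECG listings.

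**Conclusion.** The wording is loose, and no change to the plan follows. SAP 7.5 mentions Screening alone; SAP 3 and Protocol 8.2 and 8.6.4 supply the rule for the rest, and an analyst can reasonably list whatever ECGs exist. SAP 7.7 has not been shown to be false.

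The size is about 0.1 to 0.3 ET records in 50 subjects, with an 11% to 29% chance of at least one. This assumes that early stopping matches the 12-week SOF/VEL/VOX arms of POLARIS-1 and POLARIS-4 and that each early stop yields an ET ECG. The documents give no basis for counting ECGs at unscheduled visits, so those are not included. SVR12, the primary safety endpoint and every planned summary are unaffected.
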